
Research question and objectives
	
Primary objectives Compare the occurrence of hospitalization due to community-acquired pneumonia (CAP) among patients with COPD who were incident users of Trelegy 100 or MITT. Hazard ratio (HR) will be calculated to investigate if the risk of CAP in Trelegy 100 group is not higher than a certain level (HR>3) compared to MITT group.
 
Secondary objectives
 
 
a) Estimate the incidence rate of hospitalization due to CAP among COPD patients who were treated with Trelegy 100 or MITT. Overall, or incident triple use patients will be analysed in Trelegy group and MITT group, respectively.
 
b) Describe characteristics of COPD patients who were treated with Trelegy 100 or MITT. Overall, or incident triple use patients will be analysed in Trelegy group and MITT group, respectively.
 
c) Calculate crude and adjusted HRs for hospitalization due to CAP within Trelegy 100 or MITT group for each covariate, with one of the covariate subgroups serving as the reference group. Each model would be adjusted for all the other stated covariates. Overall, or incident triple use patients will be analysed in Trelegy 100 group and MITT group, respectively. In the model, following subgroups will be considered; gender, age, calendar year of Index date, month of Index date, COPD treatments in look-back period, hospitalization due to COPD exacerbation in look-back period, hospitalization due to CAP in look-back period, comorbidities of pre-defined disease such as asthma, myocardial infarction, congestive heart failure, cerebrovascular disease, dementia, peptic ulcer, peripheral vascular disease, connective tissue disease, diabetes, anxiety, depression, body mass index (BMI), smoking history, and execution of lung function test within Trelegy 100 or MITT group.
 
d) Describe change over time in the expansion of triple therapy, use of an ICS-containing medications, and proportion of asthma comorbidity among COPD patients. Over-time refers to 360 days prior to date of launch of Trelegy 100, and 0-359 days, 360-719 days, 720- 1079 days after the launch. Target population for this objective includes COPD patients regardless of treatment.
 
 
*Overall users refer to those have prescriptions of Trelegy 100 or MITT between May 22, 2019 (launch date of Trelegy 100) and May 5, 2022. The index date will be the first prescription date on or after May 22, 2019. Incident users are subpopulation of overall users who do not have any triple therapies for 360 days before the index date.

## 1. LIST OF ABBREVIATIONS AND DEFINITION OF TERMS

### List of Abbreviations

AE	Adverse event
ANOVA	Analysis of variance
ATC	Anatomical Therapeutic Chemical
BMI	Body mass index
CAP	Community-acquired pneumonia
COPD	Chronic obstructive pulmonary disease
CRO	Contract research organization
CT	Computerized tomography
DPC	Diagnosis Procedure Combination
FEV 1	Forced expiratory volume in 1 second
FF	Fluticasone furoate
ENCEPP	European Network of Centres for Pharmacoepidemiology and Pharmacovigilance
GOLD	Global Initiative for Chronic Obstructive Lung Disease
GPSP	Good Post-marketing Study Practice
GSK	GlaxoSmithKline
HAP	Hospital-acquired pneumonia
HOT	Home oxygen therapy
HR	Hazard ratio
ICD	International Statistical Classification of Diseases and Related Health Problems
ICS	Inhaled corticosteroid
IHD	Individual Human Data
IRB	Institutional review board
JRS	Japanese Respiratory Society
LABA	Long-acting beta 2 -agonist
LAMA	Long-acting muscarinic antagonist
LTRA	Leukotriene receptor antagonist
MAH	Marketing authorisation holder
MDV	Medical Data Vision Co., Ltd.
MHLW	Ministry of Health, Labour and Welfare
MITT	Multiple inhaler triple therapy
MRC	Medical Research Council
OCS	Oral corticosteroid
PMDA	Pharmaceuticals and Medical Devices Agency
PRC	Protocol Review Committee
QC	Quality control
QOL	Quality of life
SITT	Single inhaler triple therapy
SOP	Standard operating procedure
TBD	To be determined
UMEC	umeclidinium bromide
VI	vilanterol trifenate

**Definition of terms**

Term	Definition
Terms related to study design	
Study design	Study methods of choice in light of research questions. e.g., cohort design and nested case-control design
Terms for target population	
Exclusion criteria	Criteria to exclude from the target population
Inclusion criteria	Criteria for inclusion in the target population
Study population	Scope of the study group is defined by inclusion and exclusion criteria by combining information on the attributes of the study population (age, gender, presence of disease, use of drugs, etc.), location (medical institutions, etc.), time (date and time information, etc.).
Terms for duration	
At risk	Condition in which the outcome of interest can occur
Exposure period	Period starting at the index date and ending at 30 days (grace period) after the end date of the final prescription
Follow-up period	Duration of follow-up to confirm the presence or absence of an outcome in each case
Gap	Period between the prescription periods
Grace period	Period in which we consider prescription to be continuing
Index date	Key date for design: Date of start of treatment
Look-back period	Period for each covariate to be measured
Observational period	Period within which each case can be observed within the data source used
Prescription period	Period from the date of prescription until the end of treatment estimated from the package insert
Study period (data period)	Period of data extracted from the database
Terminology for analysis	
Base case analysis	Analysis to determine the results corresponding to the objective of the study
Exploratory analysis	Analysis to determine the results corresponding to the exploratory objectives
Data review	Data review performed to confirm the certainty of the code used in the definition
Sensitivity analysis	Analysis performed to confirm the robustness of the analysis results
Other	
Validation study	In the secondary use of data, the validity of the information contained in the data should be investigated in agreement with other reliable sources. Algorithms that extract specific cases, especially for injury and disease name codes, from the data are often investigated.

## Trademark Information

Trademarks of the GlaxoSmithKline group of companies
Trelegy 100 Ellipta

Trademarks not owned by the GlaxoSmithKline group of companies
Respimat hand inhaler

### 3. ABSTRACT

#### Title

Cohort study to estimate incidence of pneumonia in users of Trelegy 100 or multiple inhaler triple therapy (MITT) among patients with chronic obstructive pulmonary disease using health insurance claims data provided by Medical Data Vision Co., Ltd. (MDV) in Japan.

#### Rationale and background

The Japanese Respiratory Society (JRS) Guidelines for the Diagnosis and Treatment of Chronic Obstructive Pulmonary Disease (COPD), 5th Edition (2018 Revision) states that inhaled corticosteroid (ICS)-based drugs are used concomitantly with long-acting bronchodilators in asthma-complicated COPD. In general, the risk of developing pneumonia increases with treatments including ICS, so the use of this drug should be carefully determined according to the individual patient's condition.

Trelegy 100 is convenient because ICS, a long-acting muscarinic antagonist (LAMA) and a long-acting beta2-agonist (LABA) can be administered simultaneously with one inhalation, and the number of patients prescribed with "triple therapy" may increase compared to the past when only Multiple inhaler triple therapy was available. It is important to investigate the risks of developing pneumonia when administering drugs in clinical practice and to ensure proper use. On consultation with the Pharmaceuticals and Medical Devices Agency (PMDA), we decided to conduct a database-study for community-acquired pneumonia (CAP) requiring hospitalization.

#### Research question and objectives

##### Primary objectives

Compare the occurrence of hospitalization due to community-acquired pneumonia (CAP) among patients with COPD who were incident users of Trelegy 100 or MITT. Hazard ratio (HR) will be calculated to investigate if the risk of CAP in Trelegy 100 group is not higher than a certain level (HR>3) compared to MITT group.

##### Secondary objectives

- a) Estimate the incidence rate of hospitalization due to CAP among COPD patients who were treated with Trelegy 100 or MITT. Overall, or incident triple use patients will be analysed in Trelegy 100 group and MITT group, respectively.
- b) Describe characteristics of COPD patients who were treated with Trelegy 100 or MITT. Overall, or incident triple use patients will be analysed in Trelegy group and MITT group, respectively.
- c) Calculate crude and adjusted HRs for hospitalization due to CAP within Trelegy 100 or MITT group for each covariate, with one of the covariate subgroups serving as the reference group. Each model would be adjusted for all the other stated covariates. Overall, or incident triple use patients will be analysed in Trelegy 100 group and MITT group, respectively. In the model, following subgroups will be considered; gender, age, calendar year of Index date, month of Index date, COPD treatments in look-back period, hospitalization due to COPD exacerbation in look-back period, hospitalization due to CAP in look-back period, comorbidities of pre-defined disease such as asthma, myocardial infarction, congestive heart failure, cerebrovascular disease, dementia, peptic ulcer, peripheral vascular disease, connective tissue disease, diabetes, anxiety, depression, body mass index (BMI), smoking history, and execution of lung function test within Trelegy 100 or MITT group.
- b) Describe change over time in the expansion of triple therapy, use of an ICS-containing medications, and proportion of asthma comorbidity among COPD patients. Over-time refers to 360 days prior to date of launch of Trelegy 100, and 0-359 days, 360-719 days, 720- 1079 days

after the launch. Target population for this objective includes COPD patients regardless of treatment.

\*Overall users refer to those have prescriptions of Trelegy 100 or MITT between May 22, 2019 (launch date of Trelegy 100) and May 5, 2022. The index date will be the first prescription date on or after May 22, 2019.

Incident users are subpopulation of overall users who do not have any triple therapies for 360 days before the index date.

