### 8.3.3. Confounders and effect modifiers

#### 8.3.3.1. Covariates

The following covariates data will be used to calculate the marginal HR for hospitalization due to CAP among incident Trelegy 100 users compared to incident MITT users (primary objective), to characterize target patients (secondary objective-b) and to calculate adjusted HRs for “hospitalization due to CAP” among subgroups within Trelegy 100 or MITT groups (secondary objective-c)).

- **Sex**
- **Age:** Age at index date
- **Calendar year of index date:** Because medical practice changes over time
- **Month of index date (and not the month of hospitalization due to CAP):** Because of seasonal differences in pneumonia occurrence
- **COPD treatments in look-back period**
  - 1) Immediate previous treatment as COPD maintenance therapy (LAMA, LABA, LAMA/LABA, ICS/LABA, ICS/LAMA/LABA or no COPD maintenance therapy): As potential confounding factors
    - Immediate previous therapy will be identified during 180 days before the index date (and not during the entire look-back period).
  - 2) Prescriptions of ICS as treatment of COPD or asthma: As a risk factor for pneumonia occurrence during the look-back period  
Confirm that ICD-10 code for COPD (J42, J43 or J44) or asthma (J45 or J46) is recorded in the receipt of the month which includes prescription of ICS.
  - 3) Prescriptions of oral corticosteroid (OCS) as treatment of COPD or asthma: As a risk factor for pneumonia occurrence during the look-back period  
Confirm that ICD-10 code for COPD (J42, J43 or J44) or asthma (J45 or J46) is recorded in the receipt of the month which includes prescription of OCS.
  - 4) Home oxygen therapy (HOT) for COPD: As an index for COPD severity  
Confirm that ICD-10 code for COPD (J42, J43 or J44) is recorded in the receipt of the month which includes the conduct of HOT.
    - Other therapies (including rescue therapy, xanthine, biologicals) for COPD or asthma will not be included as covariates.

- **History of COPD exacerbation**

In MDV database, hospitalization due to COPD exacerbation (severe COPD exacerbation) will be identified correctly by using DPC data, while it is difficult to identify mild/moderate COPD exacerbation without hospitalization (i.e., without DPC data) because systemic corticosteroids/antibiotics are prescribed for various diseases and prescription data are not linked with disease data one by one.

Hospitalizations due to COPD exacerbation in the look-back period.

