- Definition: Hospitalization due to COPD exacerbation in the look-back period will be identified using DPC data. The following ICD-10 codes, DPC disease classification codes and prescription data will be used.
  - 1) Any of the following ICD-10 codes as DPC disease segment #21 (disease which triggered the hospitalization)
    - Pneumonia-related codes: J10.0, J11.0, J12-J18
    - Acute lower respiratory tract infection-related codes: J20-J22
    - COPD exacerbation-related codes: J44.1
    - Chronic respiratory failure: J96.1
  - 2) Prescription of any systemic corticosteroid combined with any systemic antibiotics at the admission day or the next day. Date of prescription with systemic corticosteroid can be the same as or different from that of antibiotics prescription.

If both of the above 1) and 2) are recorded on the same hospitalization, it is defined as “COPD exacerbation requiring hospitalization”.

Only the presence or absence of the event in the look-back period will be identified.

- **History of pneumonia**

Hospitalization due to CAP in the look-back period

- Definition: Same definition as the outcome measure (see “Sec 8.3.2 Outcome definitions”)
- Only the presence or absence of the event n look-back period will be identified.

■ **Medical history or comorbidities**

The following medical history or comorbidities in the look-back period

- Definition:  $\geq 1$  record (outpatient visit or hospital admission) with relevant ICD-10 codes for each comorbidities in the look-back period [Index date – 360 days]
  - 1) Asthma (ICD-10 codes: J45, J46)
  - 2) Myocardial infarction (ICD-10 codes: I21.x, I22.x, I25.2)
  - 3) Congestive heart failure (ICD-10 codes: I09.9, I11.0, I13.0, I13.2, I25.5, I42.0, I42.5-I42.9, I43.x, I50.x, P29.0)
  - 4) Cerebrovascular disease (ICD-10 codes: G45.x, G46.x, H34.0, I60.x-I69.x)
  - 5) Dementia (ICD-10 codes: F00.x-F03.x, F05.1, G30.x, G31.1)
  - 6) Peptic ulcer (ICD-10 codes: K25.x-K28.x)
  - 7) Peripheral vascular disease (ICD-10 codes: I70.x, I71.x, I73.1, I73.8, I73.9, I77.1, I79.0, I79.2, K55.1, K55.8, K55.9, Z95.8, Z95.9)
  - 8) Connective tissue disease (ICD-10 codes: M05–M08, M30–M36)
  - 9) Diabetes (ICD-10 codes: E10.0-E10.9, E11.0-E11.9, E12.0-E12.9, E13.0-E13.9, E14.0-E14.9)
  - 10) Anxiety (ICD-10 codes: F40-F42)
  - 11) Depression (ICD-10 codes: F32, F33)

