## 8.4. Data Sources

The proposed study will be conducted using the Japanese MDV hospital claims database. MDV is a Japanese company specializing in integrated medical systems that manages a large administrative database constructed from hospitals (mainly tertiary) in Japan. The MDV data cover around 25% of acute care hospitals in Japan (439 hospitals) and include both inpatient and outpatient services. For the cumulative period between April 2008 and February 2021, the database has over 35.7 million patients, making it one of the largest Japanese healthcare datasets.

This study will use all available data between November 2017 and Apr 2023 in the MDV hospital claims database to assess the proposed study objectives. The data is updated monthly, thereby minimizing the time lag for data access and analyses. The database contains disease diagnoses, claims for medical procedures and pharmacy prescriptions (from inpatient and outpatient services in the hospitals covered), and laboratory test results available for approximately 10% of patients. As this study will only use de-identified data, approval from an institutional review board (IRB) will not be necessary for the conduct of this study.

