#### 8.7.3.1. Primary endpoints

##### 8.7.3.1.1. HRs for hospitalization due to CAP among incident Trelegy 100 users compared to incident MITT users

To adjust covariates (refer to “8.3.3.1 Covariates”), propensity score which is defined as a probability of Trelegy 100 treatment selection conditional on observed covariates will be estimated for an individual using logistic regression. Multicollinearity will be considered when selecting covariates. By inverse probability of treatment weighted Cox models using the propensity score, the marginal HR along with 95% confidence intervals will be estimated among incident Trelegy 100 users compared to incident MITT users. Variance estimation will be calculated using robust sandwich variance method.

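### The closed comorbidity list behind the primary propensity score omits cancer, kidney, liver and non-asthma chronic lung disease, so any imbalance in them is neither adjusted for nor seen

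*Protocol*

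**What the plan says.** Protocol 8.3.3.1 ties its covariates to the primary objective: "The following covariates data will be used to calculate the marginal HR for hospitalization due to CAP". Under "The following medical history or comorbidities in the look-back period" it gives a numbered list with codes. The list starts at "1) Asthma (ICD-10 codes: J45, J46", its only respiratory item, and ends at "11) Depression (ICD-10 codes: F32, F33"), with no open category after it. Between them are myocardial infarction, heart failure, cerebrovascular disease, dementia, peptic ulcer, peripheral vascular disease, connective tissue disease, diabetes and anxiety. A condition counts if at least one record carries the code in the look-back.

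Objective c), in the abstract and Section 7, repeats the same 11 items ("comorbidities of pre-defined disease such as asthma, myocardial infarction, congestive heart failure, cerebrovascular disease, dementia, peptic ulcer, peripheral vascular disease" and so on). Its wording reads as a set of examples and it concerns HRs within each group, so 8.3.3.1 is the operative text for the primary analysis.

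Section 8.7.3.1.1 estimates the primary HR thus: "By inverse probability of treatment weighted Cox models using the propensity score". The score is built on the 8.3.3.1 covariates, and the only selection step is "Multicollinearity will be considered when selecting covariates". Section 8.7.3.2.3 judges balance by standardized differences on the same covariates. On the data source, Section 8.4 says: "The database contains disease diagnoses, claims for medical procedures and pharmacy prescriptions".

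**The concern.** An inverse-probability-weighted HR is adjusted only for what enters the propensity score. Four groups of conditions that a clinician would expect to raise the risk of a pneumonia admission are not on the list, although they could be taken from the same records by the same rule. Patients who have them are not excluded by Section 8.2.2. Because balance is checked only on listed items, an imbalance in the omitted ones would not show in the planned output.

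The study asks whether the HR exceeds 3. Section 8.5.1 defends that tolerant line partly by unaccounted-for confounding and unavailable data. The line gives some protection against a false signal, but none in the other direction: confounding that lowers the HR could hide a true HR above 3.

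**Working it through.** **Step 1: can the list grow elsewhere in the protocol?**
- 8.7.3.1.1: a multicollinearity check can remove covariates but not add them.
- 8.7.1: covariates with more than 10% missing data may be supplemented or excluded. Nothing is added.
- 8.7.3.3: the three sensitivity conditions change the COPD definition, the MITT overlap and the follow-up length. None changes the covariates.
- 8.7.3.4: the data review provides for updated codes and a revised way of identifying COVID-19, not for further covariates.
- 8.9: the limitations name lung function, symptoms, BMI, smoking and care outside the database. The omitted conditions are not mentioned.

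The list is therefore closed as written. Since the protocol itself fixes it with codes, it is not a detail left to the SAP.

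**Step 2: reproduce Table 1 (8.5.1).** Total events D = (n1 + n0) × rate, split in the ratio n1·HR : n0, and

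P(observed HR > 3) = Φ( ln(HR/3) / √(1/d1 + 1/d0) ).

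For 1935/1311 patients at 8%, D = 3246 × 0.08 = 259.7. At true HR 3.5, d1 = 217.6 and d0 = 42.1, so SE = 0.168 and P = Φ(0.154/0.168) = 82.0%, as printed. At true HR 2.5, d1 = 204.3 and d0 = 55.4, so SE = 0.152 and P = Φ(−0.182/0.152) = 11.4%, as printed. All 40 cells reproduce: those printed as numbers agree within 0.05 points, and the three cells printed as above 99.0 compute to 99.1 to 99.7. Table 1 is not in error; it takes the HR to be free of bias.

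**Step 3: illustrate one omitted binary condition.** The documents give no prevalence by group and no relative risk (RR), so these are assumptions. With prevalence p1 (Trelegy 100) and p0 (MITT) remaining after weighting:

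bias factor = [1 + p1(RR − 1)] / [1 + p0(RR − 1)].

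For RR 2, 10% v 15% gives 1.10/1.15 = 0.957 and 10% v 20% gives 1.10/1.20 = 0.917. Reversed, they are 1.045 and 1.091. Multiplying the true HR by the factor in the Step 2 formula (1935/1311, 8%) gives the probability of observing HR > 3:

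| Prevalence, Trelegy v MITT | Factor | True HR 2.5 | True HR 3 | True HR 3.5 |
|---|---|---|---|---|
| equal | 1.000 | 11.4% | 50.0% | 82.0% |
| 10% v 15% | 0.957 | 6.5% | 38.9% | 74.6% |
| 10% v 20% | 0.917 | 3.4% | 28.8% | 65.9% |
| 15% v 10% | 1.045 | 18.5% | 60.8% | 87.7% |
| 20% v 10% | 1.091 | 27.0% | 70.1% | 91.8% |

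Over a wider assumed range (RR 1.5 to 3; 10% in one group, 15% to 30% in the other) the factor runs from 0.75 to 1.33.

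**Step 4: what would matter at the threshold?** A true HR of 2.5 reaches 3 with a factor of 3/2.5 = 1.20, and a true HR of 3.5 falls to 3 with 3/3.5 = 0.857. A true HR of 2 would need 3/2 = 1.5, outside the whole range above.

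**The case against.** The strongest reply is that the list is a referenced choice. Section 8.3.3.1 says its covariates were considered in earlier studies of ICS and pneumonia in COPD and cites at least one source for each comorbidity. That stands for the items included, peptic ulcer, anxiety and depression among them. It does not explain what was left out.

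Second, the clinical premise comes from outside the documents. The risk factors named in 8.9 are age, lung function, exacerbation history, dyspnoea score and BMI; none of the omitted groups is there. This stands, and the premise must be labelled as an assumption.

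Third, a predictor of pneumonia biases the HR only if it also differs between the groups. Both groups take ICS, LAMA and LABA, the primary analysis is limited to incident users, and nothing in the protocol suggests that cancer, kidney or liver disease steers the choice of inhaler. This also stands. Equally, 8.5.1 says that the difference in patient characteristics is unknown, so balance cannot be presumed.

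Fourth, the score already holds age, earlier CAP and exacerbation admissions, oral and inhaled steroids, home oxygen, heart failure, diabetes and more. The imbalance left after weighting may be smaller than the raw prevalences used in Step 3.

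A reader might infer that the primary HR is confounded, or that the study is tilted towards reassurance. The documents support neither: confounding is possible rather than shown, and either direction is open. Nor should the fall from 50% to 28.8% be taken as the effect of the omission, since it assumes a doubled prevalence and a true HR exactly on the threshold, and ignores correlated covariates.

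**Conclusion.** The omission is real, and it lies in the section that governs the primary analysis. The propensity score and the balance table cannot deal directly with malignancy, chronic kidney disease, chronic liver disease or chronic lung disease other than asthma, and the protocol gives no reason for leaving them out.

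The harm is conditional. It requires that these conditions predict pneumonia admission and that they remain imbalanced after weighting. The documents settle neither the size nor the direction. For one condition with RR 2, an illustrative factor is 0.96 to 0.92, or 1.05 to 1.09 if the imbalance is reversed, before partial adjustment by correlated covariates. A shift of that size could affect how a true HR near 3 is read; over the whole range examined, it would not carry a true HR of 2 to the threshold. With no residual imbalance there is no bias. The point deserves action as an inexpensive improvement, not as a demonstrated error in the HR.

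**What to change.** Before data extraction, add to 8.3.3.1, under the existing rule of at least one coded record in the look-back:
- malignancy, with lung cancer as a separate item if wanted;
- chronic kidney disease;
- chronic liver disease;
- chronic lung disease other than asthma, at least bronchiectasis and interstitial lung disease.

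Carry them into the primary propensity score and the weighted and unweighted standardized differences in 8.7.3.2.3, and align the lists in the abstract and Section 7. In 8.7.3.3, add the primary HR with the 11-item list as a sensitivity analysis, so that the effect of the wider set is visible. Settle this before the extraction for the data review, because that review already tabulates CAP admissions by group.

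The cost is a few ICD-10 code groups, four or five more binary terms and slightly more variable weights. No new data source is needed.
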